The plan is to enroll from 20 to 40 children and adolescent subjects with newly-diagnosed T1DM. Twenty will be randomized to the FIXED group and twenty will be randomized to the ICR group. The subjects will be selected from children and adolescents admitted to CHOA-Egleston with a diagnosis of new-onset Diabetes Mellitus. Participation in this study will be determined by a set of inclusion/exclusion criteria.

1) Inclusion Criteria

For enrollment in the study, subjects must: (1) Have Confirmed diagnosis of T1DM based on the most recent ADA criteria [16]; (2) Be 8 - 14 years of age; (3) Begin monitoring with a glucose monitor prior to discharge from the hospital; and (4) Have the ability to understand and be willing to adhere to the study protocol. (5) English or Spanish speakers.

2) Exclusion criteria

For enrollment in the study, subjects may not: (1) Have a clinically significant major organ system disease (i.e., hypertension, hyperlipidemia, or obesity); (2) Be on glucocorticoid therapy; (3) Have Type 2 Diabetes Mellitus; (4) Have Polycystic Ovarian Syndrome (PCOS); (5) Have a BMI > 85th %ile; (6) Have Acanthosis Nigricans; (7) Have any form of renal impairment; (8) Have Cystic Fibrosis; (9) Have Glucocorticoid-, Chemotherapeutic-, or any other Medication-induced form of Diabetes; (10) Be using any basal insulin other than Glargine insulin; (11) Have cognitive impairment (> 2 grades behind age-appropriate grade in school); (12) Be in Foster Care; (13) Have any history of DFCS involvement; and (14) If female, be pregnant or breast-feeding.

C. DATA MANAGEMENT

All data, including patient demographics, history, and laboratory tests will be collected on standardized forms and entered into an electronic database, REDCap. REDCap is a HIPPA-compliant, web-based, data capturing tool used in over 130 countries. Features include user-specific credentials, data-logging, longitudinal data modeling and more. Enrolled patients will be assigned a study ID. Subjects will only be identified in REDCap by their study ID. The patient's name, MRN and study ID will be kept in a secure file in a double lock in a filing cabinet under [name] supervision in the Emory Children's Center. Records will be maintained for 10 years as required for IRB studies.

D. OUTCOME MEASURES

1) Primary Outcome Measures

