A goal of 20 patients is necessary for this study, but we will reach up to 40 participants in case there is any withdraw after consented and randomized. While the overall goal of the study is to demonstrate feasibility of a subsequent randomized controlled trial, limited efficacy testing will be performed. Given a sample size of 20 participants (10/grp), we will have greater than 90% power to detect a minimum standardized mean difference of 1.25 (i.e., approximately a 1.25 standard deviation difference) between groups. Effect sizes will be calculated for all study measures of interest and be used in future power calculations. On average, there are ~25 new type I/II diabetics diagnosed at Egleston hospital each month. Assuming an eligibility rate of 40%, 10 patients would be eligible to participate each month. Based on this, we are confident in our capacity to recruit 20 to 40 participants during the study period with the goal of having 20 participants to complete the study.

Statistical Analysis

Demographic characteristics will be summarized for both groups using means and standard deviations, medians and quartiles, or counts and percentages, as appropriate based on distribution. T-tests, Wilcoxon rank sums, and/or Chi squared tests will be used to assess differences between the two groups.

Primary Aims: Measures of feasibility (consent, retention, engagement, satisfaction, etc.), will be summarized overall and by group, when applicable.

Secondary Aim 1: Parental stress scale

The parental stress scale will be scored per the instrument's instructions. The total scores for the treatment groups will be compared in a cross-sectional fashion using t-tests or Wilcoxon rank sums tests as appropriate based on the distribution of scores. Changes in parental distress over-time will be evaluated using two-way repeated measures analysis of variance models. Models will include the main effect of treatment assignment, time (baseline, 1 month, 4 months), and the treatment X time interaction. The interaction term will serve as the primary statistical test for aim 2. Summary statistics, statistical significance, and effect sizes will be reported by group at each time point of interest, when applicable.

Secondary Aim 2: Glycemic variability

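### The stated power of over 90% for a 1.25 SD difference with 10 per group is wrong: a two-sample comparison has about 75%, and 90% needs about 1.53 SD

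*Combined protocol and SAP*

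**What the plan says.** Section 5.E, Sample Size, gives the only power statement in the document: "Given a sample size of 20 participants (10/grp), we will have greater than 90% power to detect a minimum standardized mean difference of 1.25". A parenthesis adds that this is "i.e., approximately a 1.25 standard deviation difference) between groups". No alpha, sidedness, test or within-subject correlation is attached to the figure.

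The analyses it could refer to are described under Statistical Analysis in the same section. Parental stress totals are to be "compared in a cross-sectional fashion using t-tests or Wilcoxon rank sums tests as appropriate based on the distribution of scores". Change over time is tested by repeated-measures analysis of variance at baseline, 1 month and 4 months, and "The interaction term will serve as the primary statistical test for aim 2".

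The number per arm is described in two ways. Section 5.E says "A goal of 20 patients is necessary for this study, but we will reach up to 40 participants in case there is any withdraw", and aims for 20 to complete. Section 5.B, Study Population, gives an enrolment range of 20 to 40 and then says "Twenty will be randomized to the FIXED group and twenty will be randomized to the ICR group".

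**The concern.** The sentence gives the group size, the effect size and the type of comparison, so it can be checked with only alpha left to assume. A difference of 1.25 SD is large, but 10 per group is small, and more than 90% power looked too high for that combination.

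This is the only planning figure for the efficacy comparisons. The plan intends to report statistical significance, names a main test for aim 2, predicts lower anxiety and glycemic variability in the FIXED group, and will use the observed effect sizes to plan a later trial. A reader who trusts the sentence would take a non-significant result as good evidence against a 1.25 SD difference, with a miss rate below 10%. If the true miss rate is about one in four, that inference is not justified. The mention of 20 per arm in section 5.B adds doubt about which group size the figure belongs to.

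**Working it through.** **Inputs**

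- n = 10 per group, d = 1.25, comparison between groups: section 5.E, Sample Size.
- Test: two-sample t-test or Wilcoxon rank sum: section 5.E, Statistical Analysis.
- Alpha and sidedness: not stated. Two-sided 0.05 is assumed, and other values are tried below.

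**Attempt to reproduce the stated figure**

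For a two-sample t-test, df = 2n − 2 = 18 and the noncentrality is d × √(n/2) = 1.25 × √5 = 2.795. Power is the probability that a noncentral t with these parameters exceeds the critical value.

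| Setting (10 per group, d = 1.25) | Power |
|---|---|
| t-test, two-sided 0.05 (critical value 2.101) | 75.3% |
| Normal approximation, two-sided 0.05 | 79.8% |
| Exact Wilcoxon, two-sided 0.05 (20,000 simulated trials, normal data) | about 71% |
| t-test, one-sided 0.05 (critical value 1.734) | 85% |
| t-test, one-sided 0.10 (two-sided 0.20) | 92.6% |

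Solving for alpha, the t-test reaches 90% only at a two-sided level of about 0.152. The stated figure is therefore not reproduced at any conventional alpha.

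**Size of the discrepancy (two-sided 0.05)**

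- Type II error: 1 − 0.753 = 0.247, against an implied ceiling of 0.10, so about 2.5 times as large.
- Detectable difference with 10 per group: 1.53 SD at 90% power and 1.32 SD at 80%. At one-sided 0.05, 90% power needs 1.36 SD.
- Group size needed for d = 1.25: 14 per group gives 88.9% and 15 per group gives 91%.

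**Readings under which more than 90% would be true**

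- 20 per group, the number in section 5.B: noncentrality 1.25 × √10 = 3.953, df = 38, power 97.1%. The power sentence itself specifies 10.
- A paired or one-sample t-test with n = 10: the noncentrality is again 1.25 × √10 = 3.953, with df = 9, and power is 93.9%. The sentence describes a difference between groups.
- An analysis that uses the repeated measurements. Power then depends on a within-subject correlation ρ that the plan never gives. At two-sided 0.05 with 10 per group:

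| Analysis | ρ = 0.3 | ρ = 0.5 | ρ = 0.6 | ρ = 0.7 |
|---|---|---|---|---|
| Baseline-adjusted (ANCOVA) | 78.9% | 86.0% | 90.8% | 95.8% |
| Change from baseline | 60.8% | 75.3% | 84.0% | 92.7% |
| Mean of the two post-baseline visits | 90.6% | 86.2% | 84.0% | 81.8% |
| Treatment-by-time interaction, differences 0, 1.25, 1.25 | 64.5% | 79.7% | not computed | 95.6% |

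For the interaction row, the F-test has 2 and 36 df. Its noncentrality is (n/2) × Σ(eₜ − ē)² / (1 − ρ) = 5 × 1.042 / (1 − ρ), assuming equal correlation between visits. At ρ = 0 its power is 48.6%. If the difference builds up gradually (0, 0.625, 1.25), power is 88.2% even at ρ = 0.7.

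**The case against.** Four points can be made for the plan.

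1. The primary outcomes are feasibility measures, and the plan calls the efficacy testing limited and the secondary outcomes exploratory. The power figure governs no primary endpoint, stopping rule or progression criterion. This stands, and it limits the consequences. It does not make the number correct.

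2. The 75% assumes two-sided 0.05, while the hypothesis in section 5.A is directional. At one-sided 0.05 the shortfall is about 5 points rather than 15. This also stands, and the assumption has to be declared. The sentence is still wrong under that reading.

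3. The declared main test for aim 2 is the interaction, not the two-sample test, and glycemic variability is to be analysed by multilevel models. Some of these analyses could pass 90%: ANCOVA from a correlation of about 0.6, or the mean of two visits at a low correlation. It is therefore more exact to say that the figure fails for an unadjusted comparison of two groups than that every analysis in the plan has 75% power. But the sentence names no such model and gives no correlation. For the interaction, power is below 80% at correlations up to 0.5.

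4. The 20 per arm in section 5.B can be read as the enrolment ceiling, with 10 completers per arm as the sizing basis. That reading is reasonable, and section 5.E supports it. Section 5.B nevertheless states 20 per arm without condition, directly after giving a range. Nor do expected withdrawals explain the gap: at the retention target of over 90% in section 5.D, 20 completers need at most 20 / 0.90 = 22.2, so 23 randomized.

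**Conclusion.** The concern holds. For the comparison that the sentence describes, power is 75.3% rather than above 90%, a shortfall of about 15 points, and the difference detectable at 90% is about 1.53 SD rather than 1.25. These figures assume a two-sided 0.05 t-test, normal data and 10 completers per group. The finding that the claim is wrong rests on less: no conventional alpha, one-sided or two-sided, gives 90% for an unadjusted comparison of 10 with 10. Analyses that use the repeated measurements could exceed 90%, but only under correlations that the plan does not state. The harm is confined to how the exploratory efficacy results are read and used. The primary feasibility aim is untouched. The difference between 10 and 20 per arm is mostly loose wording, but it matters here because power for 1.25 SD moves from 75% to 97% between them.

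**What to change.** In section 5.E, replace the power sentence with, for example: With 10 participants per group completing and a two-sided alpha of 0.05, a two-sample t-test has about 75% power for a standardized difference of 1.25; 90% power requires a difference of about 1.53. If the figure was meant for an adjusted or repeated-measures analysis, name that model, state the assumed correlation and show power over a range of it.

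In sections 5.B and 5.E, give one planned number randomized per arm and one planned number completing per arm, and quote the power that belongs to the latter.

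This is a change of wording. It needs no extra patients, and its only cost is a less favourable figure. If the sponsor prefers to keep 1.25 SD with more than 90% power, the target becomes 15 completers per arm. That is 30 in total: ten more than the present goal, but within the enrolment ceiling of 40.

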The primary goal of this study is to determine the feasibility of a subsequent clinical trial of rapid acting insulin dosing for fixed carbohydrates (FIXED group) vs ICR with variable carbohydrate intake (ICR group). In doing so, we will examine our ability to recruit and consent patients (>70% consent rate), study retention (>90% retention), completion of study visits (average session attendance \geq 90%), study measures (\geq 90% measure completion), caregiver treatment adherence, and post-treatment satisfaction (\geq 90%),

2) Secondary Outcomes Measures

Secondary outcome measures will include caregiver anxiety and glycemic variability. Each of these measures are described below.

One secondary outcome measure is caregiver anxiety. This will be assessed by a parental stress scale [17]. The caregiver will fill out the questionnaire at initial enrollment (prior to hospital discharge) and at each clinic follow-up throughout the study. We will use the Spanish adaptation of parental stress scale (PSS) [18] for Spanish population if necessary.

We clarify in the survey that the questions are to be answered in terms of how the caregiver-child relationship exists since the diagnosis of diabetes mellitus.

The scales are shown in **Annex 1 and 2**

Glycemic variability (GV) is another secondary outcome measure. The GV will be calculated in all subjects through the use of a glucose monitor (GM) data classification scale. Subjects will be considered to have appropriate GV if their blood glucose level is in the range of 80 mg/dL – 180 mg/dL (Group C).

The GV classification is as follows:

Group A: < 50 mg/dl.

Group B: 50 – 79 mg/dl

Group C: 80 – 180 mg/dl

Group D: 181 – 350 mg/dl

Group E: > 350 mg/dl

Safety is the last secondary outcome measure. The safety measured that will be compared in both groups include death, risk of life threatening event (i.e., severe hypoglycemia associated with seizure or altered mental status), hospitalization for diabetes complication (diabetic ketoacidosis or hypoglycemia), and risk of disability or permanent damage.

E. STATISTICAL CONSIDERATIONS

Randomization

Randomization will be performed by study statistician using random-permuted blocks of size 2 and 4. Randomization assignments will be placed in sealed, opaque envelopes to be stored. Study investigators will not be blinded to treatment assignment.

Sample Size

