Glycemic variability will be examined both as a continuous variable and a categorical variable using the ranges defined in section D. Time series analysis will be used to examine daily measures of blood glucose (obtained from patient diary's) during the study period. Variability will be measured as the probability of acute change (PAC), using methods described by Jahnig et al. (2008). Acute changes will be adjusted for time between readings. In addition, first-order autocorrelations and/or mean-square successive difference will be used to examine variation in readings as described by Jahnig. Multilevel modeling will be used to test between-group differences in variability.

Secondary Aim 3: Safety

Adverse event of interest and serious adverse events (see section D) will be summarized overall and by treatment group. For participants experiencing more than 1 episode of a specific event (e.g., severe hypoglycemia), the maximum grade and severity will be recorded. Chi-square tests will be used to compare the frequency of events between the two cohorts.

Given the exploratory nature of these secondary outcomes, we will calculate effect sizes based on the adjusted means and standard deviations or differences in proportions, when appropriate.

All analyses will be conducted using SAS v9.4 (Cary, NC).

F. ANTICIPATED RESULTS

This research will be feasible to develop a successful larger clinical trial. Due to the fixed regimen seeming to be less complicated, because there are less calculations to make than in those using the ICR group, we anticipate that parental anxiety will be decreased in the FIXED group. This will encourage more blood glucose monitoring and treatment compliance. Therefore, we anticipate GV to be decreased for the FIXED group.

G. LIMITATIONS

The major limitations of this study are related to caregiver's self-completion questionnaire and ability to contact study personnel frequently during the study period in order to report blood glucose levels and implement the insulin adjustments. More than likely, multiple insulin regimens should work, but the idea behind this study is that the fixed regimen may be easier to implement.

[figure not shown]

Figure 2: Proposed protocol.

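### Effect sizes from about 10 per arm are earmarked for future power calculations without a confidence interval or a minimum important difference; that planning use is unreliable

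*Combined protocol and SAP*

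**What the plan says.** Section 5.E, Sample Size, states: "Effect sizes will be calculated for all study measures of interest and be used in future power calculations". The basis is small: "A goal of 20 patients is necessary for this study, but we will reach up to 40 participants in case there is any withdraw", "with the goal of having 20 participants to complete the study", and the power statement uses 10 per group. Section 5.B gives the upper enrolment limit: "Twenty will be randomized to the FIXED group and twenty will be randomized to the ICR group". Section 5.E describes the enrolment above 20 as cover for withdrawals.

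The closing paragraph of Statistical Analysis returns to effect sizes for the secondary outcomes, which it calls exploratory: "we will calculate effect sizes based on the adjusted means and standard deviations or differences in proportions, when appropriate". Neither place asks for a confidence interval, a correction for small samples, a minimum important difference, or use of the SD alone. Section 5.D.1 sets the primary objective: "The primary goal of this study is to determine the feasibility of a subsequent clinical trial". Its numerical targets concern consent, retention, attendance, measure completion and satisfaction.

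**The concern.** A standardized difference estimated from 10 per arm has a standard error of nearly half an SD. Required sample size varies with the inverse square of that difference, so a modest error in it becomes a large error in the calculated size. A statistician who followed the sentence as written would enter the pilot's observed effect into the next power calculation, and nothing in the plan would signal how little it can be trusted. At stake is the next trial: it may be too small to answer its question, far larger than needed, or dropped because a small pilot happened to show nothing.

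**Working it through.** **The plan's own figure.** Section 5.E says: "Given a sample size of 20 participants (10/grp), we will have greater than 90% power to detect a minimum standardized mean difference of 1.25". Alpha, sidedness and test are not stated. With a two-sample t-test at two-sided 0.05, the noncentrality is 1.25 × √(10/2) = 2.795 on 18 df, and power is 75.3% (normal approximation 79.8%). At one-sided 0.05 it is 85.1%. The stated power is not reproduced under these settings. That is a separate matter; this point does not depend on it.

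**Inputs.** From the plan: 10 per arm, with 20 per arm as the upper limit. Assumed, because the documents are silent: true d of 0.3, 0.5, 0.8 or 1.25 (the last is the plan's own detectable difference), and a next trial with two-sided alpha 0.05 and 80% power.

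**Precision of the observed d.** SE ≈ √(2/n + d²/(4n)). At n = 10 and d = 0.5 this is √(0.200 + 0.00625) = 0.454. The noncentral-t 95% CIs are:

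| Observed d | 10 per arm | 20 per arm |
|---|---|---|
| 0.5 | −0.40 to 1.38 | −0.13 to 1.13 |
| 0.8 | −0.12 to 1.70 | 0.15 to 1.44 |

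**Effect on the next trial.**

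- Size per arm from the observed value: m = 2 × ((1.960 + 0.842)/d_obs)².
- Real power at the true value: Φ(d_true × √(m/2) − 1.960).
- Example: d_true = 0.5 and d_obs = 0.8. Then m = 2 × (2.802/0.8)² = 24.5, rounded up to 25. Real power is Φ(0.5 × √12.5 − 1.960) = Φ(−0.19), about 42%. The size needed was 2 × (2.802/0.5)² = 62.8, or 63 per arm.

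These formulas were applied to 200,000 simulated pilots per setting (normal data, 10 per arm, bias-corrected d). A next trial was assumed to follow any positive estimate. Power within half a point of 80% counted as adequate.

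| True d | n per arm needed | Zero or wrong sign | Next trial below 80% power | Below 50% power |
|---|---|---|---|---|
| 0.3 | 175 | 25% | 66% | 50% |
| 0.5 | 63 | 13% | 56% | 35% |
| 0.8 | 25 | 4% | 49% | 23% |
| 1.25 | 11 | 0.3% | 42% | 8% |

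The last two columns are conditional on a positive estimate.

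**Sensitivity.**

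- With uncorrected d, and counting only estimates above 0.05, the last two columns rise to about 71% and 55% at d = 0.3, and to about 60% and 38% at d = 0.5.
- At d = 1.25 the share below 50% power is 8–17%, depending on the estimator and on whether m is rounded up.
- With 20 per arm and d = 0.5, about 52–54% fall below 80% and 25–27% below 50%.

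**Direction of the error.** At d = 0.5 and 10 per arm the pilot overestimates d in about 49–51% of all runs. Among positive estimates (bias-corrected), the planned size has a median of 50 per arm and a 10th-to-90th percentile range of 13 to 705, against 63 needed.

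**What the pilot estimates better.** The 95% limits for the SD on 18 df are √(18/χ²) times the estimate, which gives 0.76 to 1.48. Since N varies with SD², N then ranges over about 0.57 to 2.19 times its value. That is wide, but far narrower than 13 to 705.

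**The case against.** The strongest reply is that the plan promises little. Effect sizes are to be used in future calculations, which does not exclude other inputs, and a later protocol would carry its own justification and review. Efficacy testing is described as limited. SDs and feasibility rates will be reported in any case. The percentages above rest on assumed true effects and on conditioning on a positive estimate, and they shrink as the true effect grows.

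Most of that stands, and it limits the point. Three stronger readings are tempting, and the documents do not support them.

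- A reader might infer that the pilot's stated purpose is defeated. It is not: none of the feasibility targets in Section 5.D.1 depends on an effect-size estimate.
- A reader might infer that the next trial will be sized on the point estimate alone. The text does not say so.
- A reader might infer that the next trial would be sized on an inflated estimate because only a promising pilot leads on. Selection on a significant pilot would indeed do this: at 10 per arm, every follow-on trial would be underpowered at true d of 0.3, 0.5 or 0.8. But the plan states no efficacy go/no-go rule, and its only numerical thresholds are feasibility ones. Without such selection the error runs both ways.

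The reply does not remove the core. The plan names one specific use of these estimates, adds no safeguard, and exists to prepare a later trial. The replacement inputs are also imprecise, so their uncertainty must be carried forward too.

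**Conclusion.** The concern holds as a weakness in one stated planning use, not in the feasibility objectives. Across true d of 0.3 to 1.25 at 10 per arm, among pilots with a positive estimate, sizing on the observed d for 80% power leaves roughly 42–71% of next trials short of 80% and 8–55% short of 50%. Reaching 20 per arm lessens the problem but does not cure it. The figures assume normal outcomes, two-sided 0.05 and direct use of the observed d. The true d is unknown, so the range should be read rather than any single row. The change should be made.

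**What to change.** Replace the sentence on effect sizes in Section 5.E, Sample Size, with:

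> Effect sizes will be reported descriptively with 95% CIs. The observed point estimates will not be the basis for sizing the subsequent trial, which will be powered on a justified minimum important difference. This pilot will supply the SD (allowing for its uncertainty, e.g. an upper confidence limit), the baseline–follow-up correlation with its CI, and the consent and retention rates.

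One possible SD limit is the 80% one-sided upper limit, about 1.18 times the estimate on 18 df; the choice of level is a judgement. The correlation needs its interval as well: an observed 0.5 with n = 20 has a 95% CI of about 0.07 to 0.77 (Fisher z: 0.549 ± 1.96/√17, back-transformed).

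No extra participants, visits or data are needed. The cost is that an important difference must be justified for the Parental Stress Scale and for whichever glycemic variability metric is chosen; the documents give neither difference and list several candidate metrics. The next trial's calculated size may also be larger.

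### The stress analysis has no analysis set or missing-score rule, and in its classical form the repeated measures ANOVA drops every family that misses a visit; an all-randomized mixed model should replace it

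*Combined protocol and SAP*

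**What the plan says.** Section 5.E, Sample Size, sets a target of 20 but adds that "we will reach up to 40 participants in case there is any withdraw after consented and randomized", "with the goal of having 20 participants to complete the study". The same paragraph says effect sizes from this pilot will feed future power calculations.

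Section 5.E, Statistical Analysis, Secondary Aim 1, plans two analyses of the Parental Stress Scale (PSS). One is a cross-sectional comparison by t-test or Wilcoxon test. The other is longitudinal: "Changes in parental distress over-time will be evaluated using two-way repeated measures analysis of variance models". Its terms are treatment assignment, time and their interaction, and the interaction is the designated test. Effect sizes are to be reported by group at each time point. Section 5.D has the scale completed at enrollment and "at each clinic follow-up throughout the study", so three scores per family.

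For glycemic variability the plan names a different method: "Multilevel modeling will be used to test between-group differences in variability". For stress it names none beyond the ANOVA. Section 12 monitors attrition. No section states who is analyzed, what happens to the scores of withdrawn families, or how missing scores are handled.

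**The concern.** Enrollment is sized to completers, and the named model in its classical form can use only completers. A family that leaves after its 1-month form, or misses one form, then contributes nothing, not even the scores it gave. Enrolling another family restores the count but not the comparison made by randomization.

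Dropout could plausibly relate to both arm and outcome. Section 5.E leaves investigators unblinded, families know their own mealtime regimen, the outcome is self-reported stress, and section 5.F expects the fixed regimen to be the less complicated one. If the more stressed ICR caregivers leave, the remaining ICR arm looks calmer and a benefit of FIXED is understated; if stressed FIXED caregivers leave, it is overstated. The effect sizes handed to the next trial would carry the same error.

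**Working it through.** **The plan's own figures.** Sample Size states that "we will have greater than 90% power to detect a minimum standardized mean difference of 1.25" with 10 per group. At two-sided 0.05 the noncentral t gives 75.3% (normal approximation 79.8%), so the figure does not reproduce unless unstated inputs are added. That is a separate matter and does not decide this point. The relevant figures are retention above 90% and measure completion of at least 90% (section 5.D). For 20 completers, 20/22 = 90.9% meets the retention target; 20/40 = 50% is the loss that the ceiling of 40 would accommodate.

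**Assumptions (not in the documents).** SD 1 at each visit; correlation 0.6 between every pair of visits (compound symmetry); no true effect; a fraction p of one arm, those with the highest 1-month scores, leaves before month 4; no loss in the other arm.

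**Shift among completers.** Removing the top fraction p of a standard normal lowers the mean by s = φ(z)/(1−p), with z the (1−p) quantile.
- p = 10%: 0.1755/0.9 = 0.195
- p = 20%: 0.2800/0.8 = 0.350
- p = 30%: 0.3477/0.7 = 0.497

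This is the shift at month 1. Baseline and month 4 each shift by 0.6 × s.

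| Completer bias between arms (SD) | Formula | 10% | 20% | 30% |
|---|---|---|---|---|
| Baseline-to-month-1 change | s − 0.6s = 0.4s | 0.08 | 0.14 | 0.20 |
| Baseline-to-month-4 change | 0.6s − 0.6s | 0 | 0 | 0 |
| Month-4 difference | 0.6s | 0.12 | 0.21 | 0.30 |

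The first two rows make up the interaction. The third applies to the month-4 cross-sectional test and to a month-4 effect size taken from observed scores, however the ANOVA is fitted, because leavers have no month-4 score.

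**False-positive rate of the interaction test.** Simulating 10 completers per arm under these assumptions gives about 5 to 6%, 6% and 7% at 10/20/30% loss, against about 5% with no dropout.

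**Scale of the noise.** The standard error of a single-visit difference with 10 per arm is √(2/10) = 0.45 SD, larger than any entry in the table.

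**All randomized families, by likelihood.** In large samples the bias under this dropout mechanism is about 0 for the baseline-to-month-4 contrast and the month-4 difference. If dropout instead depends on the unseen month-4 score (correlation 0.5), bias of 0.15/0.27/0.40 SD remains in both. Completers would show 0.20/0.35/0.50 SD in the month-4 difference and 0.10/0.17/0.25 SD in the baseline-to-month-4 change.

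**Missed forms.** 20 families × 3 forms = 60. Reading the 90% completion target as applying to PSS forms, 10% of 60 = 6 may be missing. If each belongs to a different family, a complete-case ANOVA keeps 14 of 20.

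**The case against.** The strongest reply is that completer-only analysis is inferred. The plan gives model terms, refers to treatment assignment and to adjusted means, and uses SAS; a mixed-model fit with those terms would fit the wording and keep partial data. That stands as a possibility, but the plan does not specify such a fit for stress, although it names multilevel modeling for the other outcome.

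A reader might infer that withdrawn families are formally replaced until 20 complete. The text supports less: enrollment up to 40, with 20 completers as a goal. Nothing says that added participants displace withdrawn ones, but nothing rules it out.

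A reader might also take the 1-month shift among completers (0.20/0.35/0.50 SD) as the bias in the planned tests. It is not. The designated test concerns change, and completers' baseline scores shift too. The 1-month cross-sectional test is unaffected in this scenario if it uses all available scores, since the leavers gave theirs.

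Finally, the outcome is secondary and exploratory, and retention is a primary feasibility measure, so differential loss should be visible. This limits the consequence. It does not supply an analysis rule, and effect sizes are meant to carry forward. Losing 6 of 20 families to missed forms is a worst case, not an expectation.

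**Conclusion.** The concern holds in a limited form: the plan leaves the stress analysis open to complete-case deletion, and a better method is available at little cost. Under the stated assumptions the designated interaction is biased by at most 0.20 SD at 30% one-arm loss, all of it in the change to month 1. The month-4 difference is biased by 0.12 to 0.30 SD. The direction depends on which arm loses its stressed caregivers.

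If retention exceeds 90%, the distortion is small beside the sampling error. The target is overall, however: 2 losses among 22 could both fall in one arm of 11 (18%), which lies just short of the 20% column. Losses nearer the 40-participant ceiling would matter more.

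The documents do not support saying that the comparison does rest on completers, or that a mixed model would remove all dropout bias. It does so only when dropout depends on observed scores. Under dropout driven by unseen month-4 scores, its baseline-to-month-4 contrast can be more biased than that of completers, which is why a sensitivity analysis belongs with it.

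**What to change.** In section 5.E, Secondary Aim 1:
- Replace the repeated measures ANOVA with a likelihood-based linear mixed model for repeated measures: the same treatment, time and interaction terms, unstructured covariance, and small-sample degrees of freedom such as Kenward-Roger.
- Define the analysis set as every randomized family in its assigned arm, using every available PSS score, including those from families who withdrew. State that added participants do not displace withdrawn ones.
- Take the by-visit effect sizes from this model.
- Add a simple sensitivity analysis, such as a delta adjustment, for dropout that depends on unseen scores, and report dropout by arm.

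In sections 5.A and 5.D, state that PSS collection continues at the existing 1- and 4-month visits for families who stop the assigned regimen but still consent to data collection.

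The cost is a few sentences and PROC MIXED in the SAS v9.4 already planned, with no added patients or visits. The downsides are the assumption about observed scores, which the sensitivity analysis addresses, and some incomplete records to handle. Follow-up data depend on the family's consent and attendance, which the plan cannot guarantee.
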